1.1 Title of study

Magnetic resonance enterography as a screening tool for axial spondyloarthritis in Crohn's disease: a prospective single-center cross-sectional observational study using MRE screening followed by clinical assessment.

1.2 Aim

The aim of this study is to determine the sensitivity and specificity of magnetic resonance enterography (MRE) as a screening tool for axial spondyloarthritis (axSpA) in a cohort of adult patients with Crohn's disease (CD) in a secondary-care hospital, using dedicated axial magnetic resonance imaging (MRI) with clinical assessment as the gold standard.

1.3 Objectives

We hypothesise that existing cross-sectional imaging (MRE) from the routine NHS care of patients with CD can be used to screen patients for evidence of axSpA, thereby prompting onward referral to the rheumatology department for further management.

The objectives of this study are therefore to determine:

1. the validity, sensitivity, specificity and area under the receiver operating characteristic (ROC) curve (AUC) of MRE as a screening tool for axSpA in CD, using dedicated axial MRI scans with clinical assessment as the gold standard.
2. the proportion of patients with evidence of axSpA on MRE imaging who fulfill the 2009 Assessment of Spondyloarthritis International Society (ASAS) criteria for axSpA, modified New York criteria for ankylosing spondylitis (AS) and the classification criteria for psoriatic arthritis (CASPAR).
3. the proportion of these patients proceeding to non-pharmacological and pharmacological treatment of their axSpA, as a surrogate measure of change in clinical care as a result of MRE screening.
4. the extra-articular features associated with axSpA in CD, in order to better characterise the clinical phenotype of enteropathic spondyloarthritis (eSpA).
5. whether the site of CD (colon, ileum, etc.) predicts the occurrence of axSpA.

1.4 Design

Prospective single-center cross-sectional observational study

1.5 Study group

The ProSpA-CD study will be divided into two parts:

ProSpA-CD-Screen Phase: Review of the patients MRE scan for evidence of axSpA

The gastroenterology team ([name]) at Cambridge University Hospitals (CUH) will write to approximately 1100 patients with a diagnosis of CD (male and female patients aged 18 years or above) who have had a MRE scan since 2015, asking for their consent to retrospectively review the MRE scans for evidence of axSpA. CD subjects with a known diagnosis of SpA (AS, axSpA, eSpA or

psoriatic arthritis) will be eligible and invited to enter the study. Subjects who consent to this will then have their MRE scans reviewed for this purpose.

ProSpA-CD-Assess Phase: Clinical assessment of case and control subjects for evidence of axSpA in the clinic setting

Patients with lesions on their MRE scan consistent with axSpA (regarded as 'cases'), but who do not have a known diagnosis of SpA, will be referred for further clinical assessment in the NHS rheumatology spondyloarthritis (SpA) clinic for evidence of axSpA ([name] NHS SpA clinic, but assessed by [name] in a supernumerary capacity). Patients will also be invited to participate in the ProSpA-CD-Assess phase of the study at this stage.

CD subjects with a known diagnosis of SpA who are already under review by rheumatology and who have lesions on MRE consistent with axSpA will be considered as cases but will instead be invited to attend the rheumatology SpA research clinic to be assessed for axSpA as this will be considered outside of their routine NHS care ([name] research clinic, but assessed by [name] in a supernumerary capacity).

CD subjects (including those with a known diagnosis of SpA) who had consented to have their MRE scans reviewed, but do not have evidence of axSpA on MRE will also be invited to participate in this phase of the study as 'control' subjects and consenting subjects will be referred for further clinical assessment in the rheumatology SpA research clinic for evidence of axSpA ([name] research clinic, but assessed by [name] in a supernumerary capacity). Cases and controls will be matched for sex and age, with a cases : control ratio of 1:1.

1.6 Study schedule

The MRE scans of consenting patients will be reviewed for evidence of axSpA in the ProSpA-CD-Screen phase of the study. Case and control subjects meeting the inclusion criteria and giving informed consent as per section 5.2.2 will then be recruited in to the ProSpA-CD-Assess phase of the study. Consented subjects will complete the following patient reported outcome measures (PROM); Bath Ankylosing Spondylitis Disease Activity Index (BASDAI), Bath Ankylosing Spondylitis Functional Index (BASFI), a Visual Analogue Score for back pain (VASbp), Ankylosing Spondylitis Disease Activity Score (ASDAS) and Stanford Health Assessment Questionnaire Disability Index (HAQ-DI). Each subject will be examined in the SpA clinic using the Bath Ankylosing Spondylitis Metrology Index (BASMI), 68 tender joint count, 66 swollen joint count, the spondyloarthritis research consortium of Canada (SPARCC) enthesitis index, and for skin or nail psoriasis.

The following investigations will also be performed *as per* standard of care for the patients with axial skeleton abnormalities on their MRE (MRE+) and no known diagnosis of SpA, if clinically indicated and if not been performed in the preceding month; full blood count (FBC), renal function, liver function tests (LFTs), C-reactive protein level (CRP), erythrocyte sedimentation rate (ESR) and faecal calprotectin. *HLA-B27* testing will also be requested if not previously performed. These investigations will also be performed for the control subjects and the group of CD subjects with a known diagnosis of SpA who are MRE+ (if not performed in the preceding month and if *HLA-B27* not previously performed) but will be funded by the research grant, unless clinically indicated.

A dedicated axial MRI scan of the spine and sacroiliac joints will be performed in all case and control subjects if indicated by the clinical assessment as part of their standard NHS care. Subjects in whom a dedicated axial MRI scan is not clinically indicated, or those who have had one performed previously for a known diagnosis of SpA, will be consented to undertake the MRI scan for research purposes and the MRI scan will be funded by the research grant.

All subjects (cases and controls) will be asked to further consent to provide research samples, including whole blood and stool, for storage and future analysis (serum for biomarker analysis, plasma for proteomic analysis, DNA for genotyping, and stool for microbiome analysis). Collection of

these samples will be funded by the existing research grant, and analysis will be funded by research grants that are currently being applied for.

The control group will receive no further follow up unless clinically indicated. CD subjects in this group with a known history of SpA will be followed up as planned by their primary rheumatology team.

The cases (excluding CD subjects with known SpA who are MRE+ and already under rheumatology review) will be followed up for their second review in the NHS rheumatology SpA clinic approximately 6 months later and will complete the following PROMs; BASDAI, BASFI, VASbp, ASDAS & HAQ-DI. Each patient will also be examined using the BASMI, 68 tender joint count, 66 swollen joint count, the SPARCC enthesitis index, and for skin or nail psoriasis. The following investigations will also be performed as per standard of care if not performed within the preceding month; FBC, renal function, LFTs, CRP and ESR. The patients will also be reviewed in the SpA clinic at an earlier date if indicated for treatment or clinical reasons. However, subjects who already have a diagnosis of SpA and are already under review by a rheumatology team will be followed up as planned by their primary rheumatology team.

Further details of how subjects will be approached, classified as cases or controls, and how the various assessments (clinical, imaging, laboratory) are being funded are detailed in [Appendix 1](#).

1.7 Study timelines & accrual

Study set up:	Up to November 2018
Recruitment and data collection:	December 2018 to February 2020
Analysis and publication of data:	March 2020 to August 2020

Please see Appendix 2 (Schedule of Procedures) and Appendix 3 (Gantt time chart for research timeline).

1.8 End of the study August 2020

2. Introduction

2.1 Background and rationale for the proposed study

Spondyloarthritis (SpA) is a term used to describe a group of chronic inflammatory musculoskeletal diseases that can present with axial and / or peripheral joint disease. SpA encompasses non-radiographic axial spondyloarthritis (nr-axSpA), AS and psoriatic arthritis (PsA). The prevalence of SpA has been estimated to range between 0.01% (Japan) and 2.5% (Alaska and Russia) of the general population [1]. There is an association with the Human Leucocyte Antigen B27 (*HLA-B27*) which is estimated to be present in 50-95% of patients with SpA [2]. Patients with SpA have an excess burden of inflammatory bowel disease (IBD), which primarily includes CD and ulcerative colitis (UC). It is estimated that up to 40% of patients with PsA also have axial disease (PsSpA) [3]. The estimated prevalence of diagnosed IBD in patients with PsSpA is 12% and in patients with AS is 10% [3]. However, few studies have investigated the presence of undiagnosed SpA in patients with IBD. SpA can have a significant negative impact on various aspects of quality of life including employment, social life and sexual relations [4-6]. PsA has been found to be associated with relatively high levels of unemployment (20%-50%) with some improvement following conventional or biologic disease modifying anti-rheumatic drugs (DMARDs) [7, 8]. Timely diagnosis and treatment is therefore potentially crucial.

Novel biologic therapies for SpA have been developed to target the dysregulated innate and adaptive immune systems which underpin its pathophysiological and inflammatory processes. Such targets include pathways involving the cytokines interleukin (IL)-17, IL12/23 and tumour necrosis factor (TNF). These cytokine pathways are also common to the pathophysiological processes of IBD [9-12]. There have subsequently been a number of biological therapies that have emerged over the last decade with a license to treat IBD and SpA, including anti-tumour necrosis factor (anti-TNF), anti-IL-23 and anti-IL 17 agents. Whilst these treatments are not equally efficacious for both conditions, if used appropriately and early in the course of the disease, they can have a significant impact on the burden of disease [13, 14].

Sacroiliitis (inflammation of the sacroiliac joints) is the radiological hallmark of axSpA, but other spinal lesions include spondylitis (inflammation of the vertebral bodies) spondylodiscitis (inflammation of the vertebral discs), enthesitis (inflammation of the spinal ligament insertion points) and the formation of syndesmophytes in chronic disease. Historically, axSpA has been diagnosed using plain radiographs of the sacroiliac joints to assess for sacroiliitis according to the 1984 modified New York criteria for AS [15]. However, over the last 20 to 30 years, cross-sectional imaging with computed tomography (CT) and magnetic resonance imaging (MRI) has become increasingly utilised. CT scans can better detect chronic bony changes in axSpA, including erosions, sclerosis and ankylosis, compared with radiographs [16-19]. However unlike MRI, they are unable to identify acute inflammatory changes related to bone marrow oedema or chronic changes related to fatty atrophy and MRI is much more effective at detecting early signs of axSpA [16, 20-22]. CT scans also pose higher ionising radiation exposure. MRI does not pose an ionising radiation risk and has therefore been recommended for the assessment of SpA in the 2009 ASAS guidelines [16]. Regarding PsA, this can be diagnosed using the CASPAR criteria [23].

The acute inflammatory changes of axSpA are best seen on MRI using dedicated fluid sensitive sequences such as a fat saturated T2-weighted sequence or a short tau inversion recovery (STIR) sequence. The typical active inflammatory lesions of the sacroiliac joint on MRI include bone marrow oedema, capsulitis, enthesitis and synovitis, and the chronic lesions include sclerosis, erosions and ankylosis [24]. The typical axSpA MRI spinal lesions include spondylitis, spondylodiscitis, enthesitis and syndesmophytes [16].

MRE imaging has been shown to be a useful tool in the diagnosis and assessment of potential complications for patients with CD [25, 26]. The majority of CD patients will have been reviewed by secondary care specialists in gastroenterology, and most will have had cross-sectional imaging in the form of MRE imaging to assess the extent of their CD. These scans also capture the axial (spine and

pelvis) skeleton but radiological assessment of this aspect of the scan is often overlooked and deemed beyond the remit of the initial MRE request. However, these scans contain valuable unreported data, which could be used to screen for the presence of axSpA in patients with CD.

To our knowledge, there have been only 12 studies assessing this in practice; the presence of axSpA features (sacroiliitis) in IBD patients as defined by cross-sectional imaging. Only two of these 12 studies have used MRE imaging for this purpose, with the majority using CT scans, and most of the studies had a small-medium sample size.

Leclerc-Jacob *et al.* (2014) assessed the MRE scans of 186 patients with IBD (131 patients with CD and 55 with UC) and found evidence of sacroiliitis in 16.7% of patients [27]. The incidence of sacroiliitis was found to be equal within the CD and UC group. Gotler *et al.* (2015) had similar findings with 15% of 286 IBD patients having evidence of sacroiliitis on MRE. However, there was no correlation between MRE score and inflammatory back pain [28]. A smaller study by Orchard *et al.* using dedicated MRI images of the sacroiliac joints found sacroiliitis in 17 of 44 (39%) patients with established CD, the majority of which had inflammatory back pain [29]. Bandyopadhyay *et al.* (2015) assessed 120 patients with IBD and found 24 patients (20%) to have sacroiliitis on dedicated MRI of the sacroiliac joints, with 21 of these patients having inflammatory back pain [30]. Chan *et al.* assessed the CT images of 216 patients with IBD compared to 108 controls. They found a significantly higher proportion of sacroiliitis in the IBD patients (15.5 vs. 5.6%) [31]. Other studies have found evidence of sacroiliitis on CT scans of patients with IBD ranging from 17% to 68% of the study group [18, 19, 32-36].

Currently, there is limited knowledge on the true prevalence of axSpA in CD patients and there is no reliable screening tool available. Undiagnosed and untreated axSpA can impact significantly on quality of life, but there are a number of potentially effective treatments which could have a significant impact on symptom burden if started in a timely fashion. The development of an effective screening tool for use within the gastroenterology clinic is therefore highly desired by the clinical and research community.

3. Study aim and objectives

3.1 Aim

The aim of this study is to determine the sensitivity and specificity of MRE as a screening tool for axSpA in a cohort of adult patients with CD in a secondary-care hospital, using dedicated axial MRI with clinical assessment as the gold standard.

3.2 Objectives

We hypothesise that existing cross-sectional imaging (MRE) from the routine NHS care of patients with CD can be used to screen patients for evidence of axSpA, thereby prompting onward referral to the rheumatology department for further management.

The objectives of this study are therefore to determine:

1. the validity, sensitivity, specificity and area under the ROC curve of MRE as a screening tool for axSpA in CD, using dedicated axial MRI scans with clinical assessment as the gold standard.
2. the proportion of patients with evidence of axSpA on MRE imaging who fulfill the 2009 ASAS criteria for axSpA, modified New York criteria for AS and the CASPAR criteria for PsA.
3. the proportion of these patients proceeding to non-pharmacological and pharmacological treatment of their axSpA, as a surrogate measure of change in clinical care as a result of MRE screening.
4. the extra-articular features associated with axSpA in CD, in order to better characterise the clinical phenotype of eSpA.
5. whether the site of CD (colon, ileum, etc.) predicts the occurrence of axSpA.

4. Study design

4.1 General

The ProSpA-CD study will be divided in to two phases:

1. **The ProSpA-CD-Screen phase:** The review of the patients MRE scan for evidence of axSpA.
2. **The ProSpA-CD-Assess phase:** The clinical assessment of case and control subjects for evidence of axSpA in the clinic setting (including clinical examination, PROMs, blood tests, stool sample testing and a dedicated MRI of the spine) followed by comparison of the two groups.

A prospective single-center observational study will be conducted. For the ProSpA-CD-Screen phase of the study, the gastroenterology team at CUH ([name]) will write to approximately 1100 patients with a diagnosis of CD (male and female patients aged 18 years or above) who have had a MRE scan since 2015, asking for their consent to retrospectively review the MRE scans for evidence of axSpA. CD subjects with a known diagnosis of SpA will be eligible and invited to enter the study. Subjects who consent to this will then have their MRE scans reviewed and those with lesions consistent with axSpA (regarded as cases), but who do not have a known diagnosis of SpA, will be referred for further clinical assessment in the NHS rheumatology SpA clinic for evidence of SpA ([name] NHS SpA clinic, but assessed by [name] in a supernumerary capacity). At this stage they will also be invited to participate in the ProSpA-CD-Assess phase of the study.

CD subjects with a known diagnosis of SpA who are already under review by rheumatology and who have lesions on MRE consistent with axSpA will be considered as cases and also invited to participate in the ProSpA-CD-Assess phase of the study. However, they will instead be asked to attend the rheumatology SpA research clinic to be assessed for axSpA as this will be considered to be outside of their routine NHS care ([name] research clinic, but assessed by [name] in a supernumerary capacity).

CD subjects (including those with a known diagnosis of SpA) who had consented to have their MRE scans reviewed, but do not have evidence of axSpA on MRE will also be invited to participate in the ProSpA-CD-Assess phase of the study as control subjects and will be referred for further clinical assessment in the rheumatology SpA research clinic for evidence of axSpA ([name] research clinic, but assessed by [name] in a supernumerary capacity). Cases and controls will be matched for sex and age, with a cases : control ratio of 1:1.

Subjects meeting the inclusion criteria and giving informed consent as per section 5.2.2 will then be recruited in to the ProSpA-CD-Assess phase of the study. Consented subjects will complete the following PROMs; BASDAI, BASFI, VASbp, ASDAS and HAQ-DI [37-40]. Each subject will be examined in the SpA clinic using the BASMI, 68 tender joint count, 66 swollen joint count, the SPARCC enthesitis index, and for skin or nail psoriasis. The following investigations will also be performed as per standard of care for the patients with axial skeleton abnormalities on their MRE (MRE+) and no known diagnosis of SpA, if clinically indicated and if not been performed in the preceding month; FBC, renal function, LFTs, CRP, ESR and faecal calprotectin. *HLA-B27* testing will also be requested if not previously performed. These investigations will also be performed for the control subjects and the group of CD subjects with a known diagnosis of SpA who are MRE+ (if not performed in the preceding month and if *HLA-B27* not previously performed) but will be funded by the research grant unless clinically indicated.

A dedicated axial MRI scan of the spine and sacroiliac joints will be performed in all case and control subjects if indicated by the clinical assessment. Subjects in whom a dedicated axial MRI scan is not clinically indicated, or those who have had one performed previously for a known diagnosis of SpA, will be consented to undertake the MRI scan for research purposes and the MRI scan will be funded by the research grant.

All subjects (cases and controls) will be asked to further consent to provide research samples, including whole blood and stool, for storage and future analysis (serum for biomarker analysis, plasma for proteomic analysis, DNA for genotyping, and stool for microbiome analysis). Collection of these samples will be funded by the existing research grant, and analysis will be funded by research grants that are currently being applied for.

The control group will receive no further follow up unless clinically indicated. CD subjects in this group with a known history of SpA will be followed up as planned by their primary rheumatology team.

The cases (excluding CD subjects with known SpA who are MRE+ and already under rheumatology review) will then be followed up for their second review in the NHS rheumatology SpA clinic approximately 6 months later and will complete the following PROMs; BASDAI, BASFI, VASbp, ASDAS & HAQ-DI. Each patient will also be examined using the BASMI, 68 tender joint count, 66 swollen joint count, the SPARCC enthesitis index, and for skin or nail psoriasis. The following investigations will also be performed as per standard of care if not performed within the preceding month; FBC, renal function, LFTs, CRP and ESR. The patients will also be reviewed in the SpA clinic at an earlier date if indicated for treatment or clinical reasons. However, subjects who already have a diagnosis of SpA and are already under review by a rheumatology team will be followed up as planned by their primary rheumatology team.

Please see Appendix 1 for study flow chart, Appendix 2 for schedule of procedures and Appendix 3 for Gantt chart of the research timeline.

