8.1 Power analysis

This study will aim to include all CD cases with MRE imaging since 2015; the estimated sample size is therefore 1100 cases.

To our knowledge, there are no studies comparing the sensitivity and / or specificity of MRE scans with gold standard dedicated MRI for the detection of sacroiliitis. However, there have been some studies comparing CT imaging with MRI and these found MRI to be up to 17% more sensitive for the detection of sacroiliitis than CT [48, 49].

Although MRE is expected to be more sensitive at detecting evidence of sacroiliitis than CT, our power calculation is based on the conservative estimate that MRE will detect at $\geq 60\%$ (sensitivity) of

the cases of sacroiliitis, when compared with the gold standard dedicated axial MRI scan. Therefore with 80% power and a two-tailed alpha of 0.05, it is estimated that ≥ 60 control subjects (MRE normal) will be required for the study. It is estimated that a sample of >60 cases (with abnormal MRE scans) would be needed since the sample size required to assess specificity for a screening test is less than that of sensitivity. Case and controls will be recruited in a ratio of 1:1. From the 1100 MRE scans already performed, it is expected that $\geq 90\%$ will have a diagnosis of CD, i.e. 990 subjects. We estimate that $\geq 50\%$ of postally invited participants will consent to participate in the study, giving approximately 445 MRE scans for review.

The two previous studies assessing IBD patients for evidence of sacroiliitis using MRE imaging estimated the prevalence to be 16.7% and 15% [27, 28]. We therefore estimate to recruit ≥ 66 subjects with positive MRE scans (cases) and ≥ 66 matched controls. This is a conservative estimate, greater than the minimum number needed to recruit.

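### Accuracy of MRE is not planned separately for patients without a prior axial SpA diagnosis, the group the referral screen is meant for

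*Combined protocol and SAP*

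**What the plan says.** **Who enters.** Section 4.1: "CD subjects with a known diagnosis of SpA will be eligible and invited to enter the study". The only exclusion criterion (5.1.2) is being unwilling or unable to consent. Sections 1.5, 4.1, 4.3.1 and 4.3.2 count known-SpA patients as cases when MRE shows lesions and allow them to be selected as controls when it does not. Section 1.5 defines known SpA as AS, axSpA, enteropathic SpA or psoriatic arthritis. On selection, "Cases and controls will be matched for sex and age, with a cases : control ratio of 1:1".

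**What the test is for.** The hypothesis in section 3.2 is that existing MRE scans can be used to screen, "thereby prompting onward referral to the rheumatology department for further management". The rationale in section 2.1 notes that "few studies have investigated the presence of undiagnosed SpA in patients with IBD". The formal aim (3.1) is wider: accuracy for axSpA among adults with CD, with no restriction to undiagnosed disease.

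**What is analysed.** Section 4.3.3 says that sensitivity, specificity and AUC will be determined. Section 8.2 covers ICCs, the percentage meeting criteria, descriptive analyses and zero-inflated regression. It names no accuracy measure. Neither section splits anything by prior SpA diagnosis. Section 8.1 plans on a single sensitivity of at least 60%, "with 80% power and a two-tailed alpha of 0.05", and gives no expected number of known-SpA patients.

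**The concern.** The protocol separates known-SpA patients for clinic, funding, letters and follow-up, but not for analysis. Section 5.2.1.2 acknowledges that those under a rheumatology team already receive care for their SpA, so a positive MRE does not prompt a new referral for them. If MRE performs differently in diagnosed and undiagnosed patients, one overall figure is a mixture whose value depends on how many diagnosed patients happen to enrol. Readers who want to know how many undiagnosed cases a referral screen would catch could not recover that from the planned output. The trial's conclusion about its stated use is therefore at stake, although the aim as worded would still be met.

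**Working it through.** **1. The plan's own figures.** Section 8.1 states that "it is estimated that ≥ 60 control subjects (MRE normal) will be required for the study" and "It is estimated that a sample of >60 cases (with abnormal MRE scans) would be needed". These minimums cannot be reproduced from the stated inputs, because no null sensitivity, comparator or interval width is given. About 60 appears only if a missing value is supplied: for example, a one-sample null of 0.42 gives 59, and a 95% half-width of 12.4 points gives 60. The expected recruitment of at least 66 cases does reproduce: 445 × 0.15 = 66.75. None of these figures allows for the mix of diagnosed and undiagnosed patients.

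**2. Inputs for the mixture.**
- Overall sensitivity: 0.60, the planning value in section 8.1.
- w, the share of reference-positives with known SpA: not in the documents; assumed 10% to 50%.
- Sensitivity of MRE in known SpA: not in the documents; assumed 50% to 90%.

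**3. Formula.** Se(overall) = w × Se(known) + (1 − w) × Se(undiagnosed), so

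Se(undiagnosed) = [0.60 − w × Se(known)] / (1 − w).

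With w = 0.3 and Se(known) = 0.80: (0.60 − 0.24) / 0.70 = 0.514. With Se(known) = 0.50: (0.60 − 0.15) / 0.70 = 0.643.

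**4. Sensitivity in undiagnosed patients when the overall value is 60%.**

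| w | known 50% | known 60% | known 70% | known 80% | known 90% |
|---|---|---|---|---|---|
| 0.1 | 61.1% | 60.0% | 58.9% | 57.8% | 56.7% |
| 0.2 | 62.5% | 60.0% | 57.5% | 55.0% | 52.5% |
| 0.3 | 64.3% | 60.0% | 55.7% | 51.4% | 47.1% |
| 0.4 | 66.7% | 60.0% | 53.3% | 46.7% | 40.0% |
| 0.5 | 70.0% | 60.0% | 50.0% | 40.0% | 30.0% |

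The gap is zero when the two sensitivities agree and changes sign around that point. It is small at w = 0.1 (at most 3.3 points here) and large only when w and the difference in sensitivity are both large.

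**5. Precision cost of a split.** Assume 60 reference-positives and w = 0.3, so 60 × 0.7 = 42 are undiagnosed. At 51.4% sensitivity, about 22 of 42 would be detected. The Wilson 95% interval for 22/42 is 38% to 67% (29 points wide), against 47% to 71% (24 points) for 36/60 overall.

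The table concerns sensitivity only. Specificity and AUC can also differ between the groups, but the documents give nothing from which to illustrate that.

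**The case against.** **The aim covers all adults with CD.** This stands. The all-subject estimate is the right answer to section 3.1 and should be kept. It does not by itself answer the referral hypothesis in section 3.2.

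**A reader might infer that pooling overstates accuracy in the target group.** The documents do not support a direction. Established disease may be easier to see, but treated disease may show less inflammation, and the table shows the sign reversing. The 60% is also a planning assumption, not a success threshold, so reaching it triggers no decision.

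**A reader might infer that known-SpA patients cannot benefit from the screen.** That goes too far. Known SpA includes psoriatic arthritis, and section 2.1 puts axial involvement at up to 40% of those patients, so some may have unrecognised axial disease. Section 4.3.2 also sends findings and outstanding plans to the existing rheumatologist. In addition, scans date from 2015 while recruitment starts in December 2018 (1.7), so some patients known at invitation may have been undiagnosed when scanned.

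**A reader might conclude that the restricted group should be the sole primary population.** That does not follow. With 66 cases, removing six (9%) leaves 60, which no longer exceeds 60 as section 8.1 requires. Controls are matched to all enrolled cases, so restriction would also break the matching.

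**Safeguards exist.** MRE readers are blinded to co-morbidities other than CD (4.2.1), and two independent radiologists read the dedicated MRI (4.3.3). These limit reader bias but do not make accuracy equal across the two groups. No blinding of the clinical assessor to a prior diagnosis is described. That is a separate matter, which stratification would not cure.

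**Conclusion.** The point holds as a gap in the analysis plan. Known-SpA patients enter both arms of the accuracy comparison, and no accuracy result is planned by prior diagnosis. That one overall figure will be reported is inferred from the case and control definitions and from the absence of any split; the documents do not state it. An overall sensitivity of 60% would be compatible with 51.4% or about 64% in undiagnosed patients at a 30% known-SpA share, depending on whether known-SpA sensitivity is 80% or 50%. The share and the known-SpA sensitivities are assumptions, so neither the size nor the direction of any difference can be fixed from the documents. The calculation also sets aside the separate question of how drawing controls 1:1 from the MRE-negative pool affects sensitivity. What can be said is that the planned output does not show whether the referral use is supported. This is a low-cost improvement to the analysis, not a reason to change who is enrolled.

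**What to change.** In section 8.2:
- State the all-subject sensitivity, specificity and AUC as the result for the aim in section 3.1.
- Pre-specify the same three measures, with confidence intervals, separately for subjects with and without a prior axial SpA diagnosis.
- Define that status at the date of the MRE scan where records allow, and say how it is assigned where they do not.
- State that any conclusion about MRE as a screen that prompts referral rests on the group without a prior diagnosis.

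Enrolment, clinical procedures and matching stay as they are. Known-SpA status is already needed for the separate invitation letters; the added work is dating the diagnosis, noting whether it was axial, and producing one stratified table. The statistical cost is the wider interval in the group without a prior diagnosis, as illustrated in the working.
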